#### **Secondary objectives**

2.To determine whether the effect of treatment on the primary analysis is different depending upon ALOX5 status (5/5 vs. 5/x and x/x).

3.To determine whether intermittent treatment with oral montelukast in preschool children reduces the time to first medical attendance.

4.To determine whether intermittent treatment with oral montelukast in preschool children reduces the need for each type of medical attention for wheeze: hospital admissions; hospital attendance; and GP visits.

5.To determine whether intermittent treatment with oral montelukast in preschool children reduces the time to first occurrence of each type of medical attention for wheeze: hospital admissions; hospital attendance; and GP visits.

6.To determine whether intermittent treatment with oral montelukast in preschool children reduces the duration of hospital admissions.

7.To determine whether intermittent treatment with oral montelukast in preschool children reduces the number of episodes, duration and time to first event of wheeze and cold.

8.To determine whether intermittent treatment with oral montelukast in preschool children reduces the need for alternative medications (Steroids, Salbutamol).

9.To describe the safety profile of montelukast.

10.To describe parents opinion of treatment efficacy

11.To describe compliance to medication

12.To determine whether baseline urinary eicosanoid level is different across baseline groups: ALOX5 status (A or B), leukotriene genes and, type of wheeze (episodic, multitrigger). **NOTE ANALYSIS DETAIL NOT CONTAINED IN THIS PLAN**

13.To determine whether montelukast is cost effective. **NOTE ANALYSIS DETAIL NOT CONTAINED IN THIS PLAN**

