#### **Secondary outcomes**

#### **Breakdown of unscheduled medical opinion**

Hospital admissions:

- Number of hospital admissions over the 12 month period as recorded at each phone call
- Duration of hospital admissions as recorded at each phone call
- Time from randomisation date to date of first hospital admission as recorded at each phone call

Hospital admission for wheeze:

- Number of hospital admissions over the 12 month period as recorded at each phone call
- Time from randomisation date to date of first hospital admission as recorded at each phone call

Hospital attendance for wheeze:

- Number of hospital attendances (A&E) over the 12 month period as recorded at each phone call
- Time from randomisation date to date of first hospital attendance (A&E) as recorded at each phone call

Unscheduled GP visit for wheeze:

- Number of unscheduled GP visits over the 12 month period as recorded at each phone call
- Time from randomisation date to date of first unscheduled GP visit as recorded at each phone call

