### **Method for handling clustering effects**

Some outcomes are collected at the level of episode, (duration of wheeze episode, duration of cold episode, duration of hospital admission) therefore we have episode data within children. In these cases a random effect is included for child.

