### **Method for handling non-adherence**

Analysis of all primary and secondary outcomes will be performed on an intention-to-treat basis. A Complier Average Causal Effect (CACE) analysis and per protocol analysis will also be conducted for the primary analysis.

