**Number of:**  
**Wheeze episodes**  
**Cold episodes**  
**Days wheezing**  
**Returned used medication sachets**

**Duration of:**  
**Wheeze episodes (days)**  
**Hospital admission (days)**

---

Data are mean (SD)

 Data are analysed using Poisson regression with fixed effects for stratification factor and treatment group a random effect for individual to account for overdispersion with follow up time fitted as the exposure. Duration of each hospital admission is analysed using Poisson regression with fixed effects for stratification factor and treatment group a random effect for individual with follow up time fitted as the exposure.

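### Length of hospital stay is compared only among admissions that occurred, so its rate ratio is not a randomised comparison, and total hospital days per child are not compared

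*SAP*

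**What the plan says.** Objective 6 (Secondary objectives) asks whether montelukast "reduces the duration of hospital admissions". The matching outcome, under Breakdown of unscheduled medical opinion, is "Duration of hospital admissions as recorded at each phone call".

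Three places fix the unit of analysis as the admission:

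- Method for handling clustering effects lists duration of hospital admission among the episode-level outcomes, says "therefore we have episode data within children", and adds a random effect for child.
- Descriptive statistics for the secondary outcomes gives average duration of episode as the summary.
- Footnote 1 to Table 4 states "Duration of each hospital admission is analysed using Poisson regression", with a child random effect and follow-up time as exposure.

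The Secondary analysis section says only that the primary analysis is repeated for duration in days of hospital admission. Alone, that could mean a total per child, but the three places above rule it out.

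Table 4 is headed as the ITT population, which the SAP defines as all participants randomised. Method for handling non-adherence says "Analysis of all primary and secondary outcomes will be performed on an intention-to-treat basis".

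Objective 4 asks whether treatment "reduces the need for each type of medical attention for wheeze: hospital admissions; hospital attendance; and GP visits". Admission counts (Table 3) and time to first admission (Table 5) are compared in the whole cohort. Table 4 has a row for days wheezing and Table 6 one for total salbutamol puffs per year. No table has a row for total days in hospital, and no supporting analyses are planned for secondary outcomes.

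**The concern.** Being admitted happens after randomisation, and treatment is expected to change how often it happens. A model with one record per admission conditions on that event. If the admissions that treatment prevents differ in length from those it does not, the remaining admissions differ between arms even when treatment changes no individual stay. Randomisation does not protect the comparison, yet the table presents it as an ITT result with a confidence interval and p-value.

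Neither model term repairs this. The child random effect handles correlation between one child's admissions, not which children enter the model. The follow-up exposure leaves never-admitted children out.

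At stake is how objective 6 is read. A per-admission ratio above or below 1 could be taken as an effect of montelukast on hospital stay when it reflects only which admissions were prevented.

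**Working it through.** The SAP states no admission rate, length of stay or number of hospital days, so there is no figure of its own to reproduce here. Every input below is an assumption. The 33% reduction is borrowed from Sample size determination, where it applies to attacks requiring medical attention, not to admissions.

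**Set-up.** Control admissions are a share *p* of short stays (1 day) and 1 − *p* of long stays (*L* days). Treatment prevents a fraction *c* of short and *d* of long stays and leaves the length of the others unchanged. Per control admission:

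- admission ratio: A = p(1 − c) + (1 − p)(1 − d)
- control days: D0 = p + (1 − p)L
- treated days: D1 = p(1 − c) + (1 − p)(1 − d)L
- per-admission ratio = (D1 / A) / D0
- total-days ratio = D1 / D0 = A × per-admission ratio

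**Base mix:** p = 0.6, L = 4, so D0 = 0.6 + 0.4 × 4 = 2.20 days.

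| Prevented (short / long) | A | D1 | Mean stay, treated | Per-admission ratio | Total-days ratio |
|---|---|---|---|---|---|
| 45% / 15% | 0.33 + 0.34 = 0.67 | 0.33 + 1.36 = 1.69 | 2.52 | 1.15 | 0.77 |
| 33% / 33% | 0.402 + 0.268 = 0.67 | 0.402 + 1.072 = 1.474 | 2.20 | 1.00 | 0.67 |
| 0% / 50% | 0.60 + 0.20 = 0.80 | 0.60 + 0.80 = 1.40 | 1.75 | 0.80 | 0.64 |

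**Range.** Take p = 0.5, 0.6 and 0.8 with L = 3 and 4.

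- *Mainly short stays prevented.* Here c is 45% or 50%, and d is set so that admissions fall by 33%. At p = 0.8, d is zero and admissions fall by 36% or 40%. The per-admission ratio runs from 1.09 (p = 0.5, L = 3, c = 45%, d = 21%: 1.46 / 0.67 = 2.18, against 2.00) to 1.25 (p = 0.8, L = 4, c = 50%, d = 0: 1.2 / 0.6 = 2.00, against 1.60). Total-days ratio: 0.71 to 0.81.
- *Prevention unrelated to stay (33% of each).* Per-admission ratio 1.00, total-days ratio 0.67.
- *Only long stays prevented (half of them).* Admissions fall by 25%, 20% or 10% at the three values of p. Per-admission ratio 0.80 to 0.87, total-days ratio 0.60 to 0.79.

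Treatment shortens or lengthens no individual stay in any scenario, yet the per-admission ratio runs from 0.80 to 1.25. That total days fall throughout follows from the set-up, since admissions are only removed. The contrast shows that the per-admission ratio does not track hospital burden.

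**The case against.** The planned analysis matches the objective as worded: objective 6 concerns the duration of admissions, not total days, and a ratio above 1 would truthfully describe the admissions that occurred. That stands as description. It does not make the ratio an effect of treatment, which is how an IRR with a p-value under an ITT heading will be read.

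A reader might infer that the plan would report a working drug as harmful, or answer objective 6 with the wrong sign. The documents do not support that. Admission counts are compared in the whole cohort, and the SAP commits to reporting every comparison. In the first row of the table above, an admission ratio of 0.67 would stand beside the stay ratio of 1.15, and their product is 0.77. Much of the benefit would be visible. What the reader could not obtain from the two separate results is a confidence interval for that product.

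The direction of bias is also unknown, because nothing in the SAP says which admissions montelukast would prevent. The outcome list places duration under all hospital admissions, not under the separate block for wheeze, so a 33% cut may be generous.

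The ITT statement sits under non-adherence, and each admission is still analysed in its allocated arm. Even so, the SAP's ITT definition covers all randomised participants, and this row does not.

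**Conclusion.** The point holds as one of interpretation and omission in a secondary outcome; the primary analysis is unaffected. That the comparison is conditional on a post-randomisation event needs no numerical assumption: it follows from the unit of analysis and objective 4.

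The size does rest on assumptions. Under the mixes shown, the per-admission ratio lies between about 0.80 and 1.25 with no change to any stay, and is 1.00 if prevention is unrelated to length. The whole-cohort admission results mitigate this without replacing a randomised comparison of hospital days. It would go too far to say that the bias runs towards harm, or that the per-admission result must be removed.

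**What to change.** - Add a row for days in hospital to Table 4, beside days wheezing. Define it as total days per child over follow-up, zero if never admitted, in all children with follow-up. Analyse it with the primary model, with follow-up time as exposure and genotype as covariate. Name it as the randomised comparison of hospital stay.
- State whether it counts all admissions or those for wheeze, and how a same-day discharge is counted.
- Keep length per admission, but label it as conditional on admission and not an ITT comparison, to be read beside the admission-rate IRR in Table 3.

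The cost is some SAP wording and one table row. Admission and discharge dates are already collected (Follow up, Unscheduled medical attendance), and the SAP says it was written before trial data were examined. Total days will have many zeros and a long tail; the negative binomial alternative already allowed in the primary model checks is available if the fit is poor. The downside is one more secondary comparison in a plan without multiplicity adjustment. It combines number and length of admissions and so overlaps objective 4.

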## **ANALYSIS OF SECONDARY OUTCOMES**

### **Definition of outcome measure**

individual type of medical attendance: (hospital admission, hospital attendance (a&e), and GP visit)

Duration (in days) of hospital admission

Number of wheeze episodes

Total duration of wheeze episode

The number of steroid (OCS) courses per year

The number of IMP courses per year

first hospital admission

first hospital attendance (A&E)

first GP visit

first episode of wheeze

proportion receiving no steroids (OCS) vs. any during the trial

Proportion starting steroids (ICS) during the trial

Salbutamol use per year

Salbutamol use per episode of wheeze per year

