### **Secondary analysis**

The primary analysis will be repeated for each of the following secondary outcomes:

individual type of medical attendance: (hospital admission, hospital attendance (a&e), and GP visit)

Duration (in days) of hospital admission

Number of wheeze episodes

Duration of wheeze episode

The number of steroid (OCS) courses per year

The number of IMP courses per year

Time to event data will be summarised using Kaplan Meier plots. The treatment effect will be evaluated using a Cox regression model. The Hazard Ratio (HR) for the treatment effect and corresponding 95% confidence interval will be presented. A

HR of less than 1 indicates a benefit of Montelukast in reducing the time to first event.

first hospital admission

first hospital attendance (A&E)

first GP visit

first episode of wheeze

Binary outcomes will be analysed with logistic regression

proportion receiving no steroids (OCS) vs. any during the trial

Proportion starting steroids (ICS) during the trial

Assumption checks and actions to be taken is assumptions do not hold

The assumption of proportional hazards for the cox regression model will be checked using the methods proposed by Grambsch and Therneau. If this assumption is violated, alternative methods will be used.

See section 8.4 for Poisson regression assumption checks.

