**Table 6: Medication usage**

ITT population	Montelukast N=	Placebo N=	IRR or OR (95% CI)	p-value
Steroids (OCS)				
 Number of courses, mean (SD)				
 Proportion receiving OCS, N (%)				
Steroids (ICS)				
 Proportion starting, N (%)				
Salbutamol				
 Number of puffs used per episode, mean(SD)				
Total puffs used per year				
Investigational Medicinal Product				
 Number of initiations, mean (SD)				
 Number of sachets per episode, mean (SD)				
Number of sachets used per year				

Data are analysed using Poisson regression with fixed effects for stratification factor and treatment group and a random effect for individual to account for overdispersion with follow up time fitted as the exposure.

Data are analysed using logistic regression with fixed effects for stratification factor and treatment group

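### Per-episode outcomes (length of each admission or wheeze episode, puffs and sachets per episode) are modelled with the child's follow-up time as exposure, so the reported IRR is not a per-episode ratio

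*SAP*

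**What the plan says.** - **Primary analysis.** The model is a Poisson regression with each child's follow-up time as exposure and a random effect for the individual. The outcome is a count per child.
- **Secondary analysis.** "The primary analysis will be repeated for each of the following secondary outcomes". The list includes the duration in days of hospital admission and the duration of wheeze episode.
- **Appendix Table 4, footnote 1.** The follow-up exposure is stated for the table, which has a duration row for wheeze episodes. A separate sentence covers admissions: "Duration of each hospital admission is analysed using Poisson regression with fixed effects for stratification factor and treatment group", with a "random effect for individual with follow up time fitted as the exposure".
- **Appendix Table 6, footnote 1.** The model has "a random effect for individual to account for overdispersion with follow up time fitted as the exposure". The marked rows include "Number of puffs used per episode, mean(SD") and "Number of sachets per episode, mean (SD").
- **Method for handling clustering effects.** Durations of wheeze episodes, cold episodes and admissions are described as episode data within children, and a random effect for child is added. Nothing there removes the exposure.

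No section switches the exposure off for a per-episode outcome.

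**The concern.** An exposure term belongs in a model when the outcome grows with time at risk. The number of admissions in a year does; the length of one admission does not. With log follow-up as offset, a 2-day admission enters as 12 days per year for a child followed for 2 months and as 2 days per year for a child followed for 12 months. The stay is the same, yet the modelled value differs sixfold.

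The random effect for child does not repair this. Follow-up time is constant within a child, so the distortion lies between children, which is where the arms are compared.

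At stake is the meaning of the estimate for the objective on duration of hospital admissions, for the duration part of the wheeze objective, and for the per-episode rows on salbutamol and trial medication. Each mixes what happens in an episode with how long the child was retained. The withdrawal reasons listed in the SAP include adverse events and perceived lack of efficacy, so retention could differ by arm. The Multiple comparisons section states that all comparisons will be reported without adjustment, so these ratios will be published.

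**Working it through.** **Follow-up figures (SAP, Methods for withdrawals, loss to follow-up and missing data).** The counts add up: 1134 + 29 + 12 + 172 = 1347, or 84.2%, 2.2%, 0.9% and 12.8%. The 29 + 12 = 41 children without data contribute no episodes, so the relevant share is the 172 with partial follow-up (12.8%), not all 213 with incomplete data (15.8%). No split by arm is given.

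**What the model estimates.** Leaving the random effect aside, a Poisson model with offset log(follow-up) estimates, in each arm, (sum of episode durations) / (sum of follow-up time over episodes). Therefore

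IRR = (true per-episode ratio) / (F1 / F0),

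where F is the mean follow-up over episodes in each arm. Without the offset, the IRR is the per-episode ratio.

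**Size of F1 / F0.** Assumptions, not in the SAP: a share p of children has follow-up uniform over 2 to 12 months, the rest have 12 months, and episodes occur at the same rate in both arms. A child contributes episodes in proportion to follow-up t, so F = E[t²] / E[t]. In years, the partial group has E[t] = (1/6 + 1)/2 = 0.5833 and E[t²] = (1 − 1/216)/(3 × 5/6) = 0.3981. Hence

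F(p) = (1 − p + 0.3981p) / (1 − p + 0.5833p).

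This gives F(0.10) = 0.9398/0.9583 = 0.9807, F(0.12) = 0.9766, F(0.16) = 0.9683, F(0.20) = 0.9596, F(0.22) = 0.9551 and F(0.26) = 0.9460.

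With a true per-episode ratio of 1.00:

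| Partial follow-up, montelukast vs placebo | IRR with the exposure |
|---|---|
| 13% vs 13% | 1.00 |
| 16% vs 10% | 0.9807/0.9683 = 1.013 |
| 20% vs 12% | 0.9766/0.9596 = 1.018 |
| 22% vs 10% | 0.9807/0.9551 = 1.027 |
| 26% vs 0% | 1/0.9460 = 1.057 |

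Swapping the arms inverts the ratio.

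**With the random effect.** The weighting of children changes, and the shift is similar or somewhat larger. Large-sample simulations with a gamma child effect, 2 episodes per year and a mean of 3 days per episode (all assumed) gave:

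| Montelukast vs placebo | With exposure | Without |
|---|---|---|
| 13% vs 13% | 1.005 | 0.999 |
| 10% vs 16% | 0.988 | 1.006 |
| 21% vs 5% | 1.051 | 1.001 |
| 0% vs 26% | 0.922 | 1.003 |

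**Type I error.** These simulations used 650 per arm and 0.76 episodes per year with SD 1.22 (the SAP's sample size inputs), 3 days per episode (assumed), no true effect, and 500 or 600 runs per scenario.

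- 13% vs 13%: IRR 1.00, rejection 4.8-6.5%.
- 16% vs 10%: IRR 1.01-1.02, rejection 5.0-7.0%.
- 20% vs 12%: IRR 1.02-1.03, rejection 6.8-8.8%.
- 22% vs 10%, in either direction: a shift of 3-5%, rejection 8.5-14.2%.

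In the 500-run set, the same model without the exposure rejected in 6.2-7.0% of runs at the 20%/12% split, so not all of the excess over 5% there comes from the offset. The Monte Carlo standard error is about 1 percentage point: √(0.088 × 0.912/500) = 1.3 points.

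**The case against.** The best defence concerns consequence. The trial is double-blind, the SAP gives no follow-up by arm, 44 of the 172 partial cases had not formally withdrawn and are being queried, and the SAP expects completeness to improve. With equal follow-up the offset cancels in expectation. All of this stands, and it limits the size of the problem. It does not make the estimate a per-episode ratio.

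Several stronger readings are tempting, and the SAP does not support them:

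- *Dropout as such biases the treatment ratio.* Only a difference in follow-up between arms does so in expectation.
- *The type I error doubles to about 10%.* That needs a split near 22% vs 10%, and nothing in the SAP documents such a split. If admissions were rarer, say 0.2 per year (assumed), rejection at 20% vs 12% was 5.0%.
- *The whole plan is affected.* The primary outcome, its subgroup analyses and the per-child counts use the exposure correctly.
- *The Secondary analysis section fixes the model for puffs and sachets per episode.* Its list contains neither, so for these two the error rests on Table 6 alone. The outcome name "Salbutamol use per episode of wheeze per year" mixes two scales but specifies no model.

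It can also be said that the SAP means a per-child total, because the definitions under Analysis of secondary outcomes refer to the total duration of wheeze episode. An exposure would suit a total. However, the Secondary analysis list, the clustering section and the duration row of Table 4 all refer to the episode, and the wheeze total already has its own Table 4 row, days wheezing. For admissions, the footnote says explicitly that each admission is the unit.

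**Conclusion.** Wrong as written, and it should be fixed; secondary outcomes only. For four outcomes (length of each admission, length of each wheeze episode, puffs per episode, sachets per episode) the stated model estimates the per-episode ratio divided by the follow-up ratio of the arms.

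The likely distortion is small: none if follow-up is balanced, about 1-2% at 16% vs 10%, about 2-3% with type I error of roughly 7-9% at 20% vs 12%, and more only at extreme splits. It makes episodes look longer, or use per episode higher, in the arm with shorter follow-up.

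These sizes rest on an assumed uniform distribution of partial follow-up, assumed splits by arm and an assumed mean of 3 days. The 12.8% refers to phone-call data. For the diary outcomes, the Derived and computed variables section ties observation to staying on medication, so their share of shortened observation may differ, and the SAP does not give it. The misspecification itself needs none of these assumptions.

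**What to change.** 1. Remove the follow-up exposure from the per-episode rows of Appendix Tables 4 and 6, and from the two duration outcomes in the Secondary analysis list. Keep the random effect for child and the stratification covariate.
2. Keep the exposure for per-child counts and totals, including the days wheezing row already in Table 4.
3. Reconcile the total duration of wheeze episode (Definition of outcome measure) with the duration of wheeze episode (Secondary analysis), so that the unit is clear.

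The cost is two footnotes, one clause in the text and one model option per outcome. No new data are needed. Because the SAP states that it was written before trial data were examined, the change can be made without knowledge of results.

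Optional, and not part of the correction: total hospital days per child (zero if never admitted) with follow-up as exposure. This would be a new outcome with a different estimand.
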